9.12 Concomitant Medications

Concomitant medications are prescription medications, over-the-counter (OTC) drugs or dietary supplements taken by a patient. Concomitant medications should be collected at Visit 1 and should include any medications that, in the opinion of the Investigator, could contribute to dry mouth.

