5.3 Handling of Missing Data

All attempts will be made to limit the amount of missing data. Unless otherwise specified, no attempt will be made to impute missing data. If a data point is missing, that data point will not contribute to that portion of the analysis. The number of evaluable observations will be reported so that the extent of missing data can be assessed.

In the case of a date (such as partial adverse event onset or death), the unknown portion of the date will be imputed. If the month and year are known, the 15th of the month will be used for analysis. If only the year of birth is known, date of birth will be analysed as if it occurred on 30th June of the known year. In all other cases, unknown dates will be referred to study sites for resolution.

Imputation of partial dates is subject to the condition that it must occur on or after the date of Visit 1. In the case where the imputed date is prior to the date of Visit 1, the date of Visit 1 will be used.

Since death cannot occur before any documented subject contact, for date of death the imputed date of death must occur on or after last known contact in study.

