5.9 Subgroup Analyses

Analyses will be stratified by study site. Subgroup analysis of the primary endpoints will be carried out for sex and age group (below the median age of the study sample versus above the median age). These analyses are intended to demonstrate consistency of results across subgroups.

Heterogeneity between subgroups will be examined in a regression model that includes the treatment, subgroup and their interaction. Additional exploratory analysis may be performed to understand any variations in the outcomes between subgroups.

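### SAP 5.3 puts a Visit 1 lower limit on all imputed dates without exempting date of birth, so as written it cancels its own birth-date rule and gives age 0

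*SAP*

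**What the plan says.** SAP 5.3 sets out its date rules in this order.

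- Scope: "In the case of a date (such as partial adverse event onset or death), the unknown portion of the date will be imputed". Adverse event onset and death are given as examples; the rule covers dates in general.
- Day missing: "If the month and year are known, the 15th of the month will be used for analysis". This is not tied to any type of date.
- Birth year only: "If only the year of birth is known, date of birth will be analysed as if it occurred on 30th June of the known year".
- Anything else: "In all other cases, unknown dates will be referred to study sites for resolution".
- Lower limit, in the next paragraph: imputation of partial dates must give a date no earlier than Visit 1, and "In the case where the imputed date is prior to the date of Visit 1, the date of Visit 1 will be used".
- Death: one further condition, that the imputed date may not precede the last known contact.

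Death is the only type of date with a condition of its own attached to the limit. Date of birth has none.

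Age is used in two places. SAP 5.5 promises descriptive statistics for baseline demographics. SAP 5.9 plans a subgroup analysis of the primary endpoints split at the sample median age, with a regression model containing the treatment-by-subgroup interaction. Protocol 8.3 requires participants to be at least 18.

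**The concern.** Date of birth is one of only two imputation cases that SAP 5.3 spells out, and the Visit 1 limit follows directly after it. An adult's birth date always precedes Visit 1. A programmer who applies the section as one routine to every partial date would first set a year-only birth date to 30 June and then replace it with the date of Visit 1. The two instructions cannot both have effect for any eligible patient.

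At stake are the age line of the baseline table and the assignment of patients to the two age groups in SAP 5.9. No primary result depends on it.

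**Working it through.** There is no figure in the plan to reproduce. The check applies the rule as written.

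**Inputs from the documents.** Year-only birth date becomes 30 June (SAP 5.3). Imputed dates before Visit 1 become Visit 1 (SAP 5.3). Minimum age is 18 (Protocol 8.3). Planned enrolment is 42 (Protocol 15.1, SAP 4).

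**Assumed.** Age is derived from date of birth as of Visit 1. Visit 1 is taken as 10 March 2022 for illustration; the zero result does not depend on this date.

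**Step 1: age for one patient.** Imputed date = 30 June of the birth year. Date used = the later of the imputed date and Visit 1. Age = (Visit 1 − date used) / 365.25.

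| Birth year | Age from 30 June rule alone | Age with the Visit 1 limit |
|---|---|---|
| 1940 | 81.7 | 0.0 |
| 1960 | 61.7 | 0.0 |
| 1980 | 41.7 | 0.0 |
| 2003 | 18.7 | 0.0 |

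With the limit, the date used is always Visit 1, so age = (Visit 1 − Visit 1) / 365.25 = 0. A birth date known by month and year is set to the 15th and then meets the same limit, with the same result. Without the limit, the 30 June rule is off by at most 184 / 365.25 = 0.5 year.

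**Step 2: mean age.** Suppose the true mean is 60, also among the patients with imputed birth dates (assumed). With k imputed birth dates among 42, the reported mean is 60 × (42 − k) / 42:

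- k = 1: 58.6
- k = 5: 52.9
- k = 10: 45.7
- k = 42: 0

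**Step 3: median-age split.** The documents do not give the share of partial birth dates, so a range is shown.

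- 10%: 0.10 × 42 = 4.2, about 4 patients
- 20%: 0.20 × 42 = 8.4, about 8 patients
- 50%: 0.50 × 42 = 21 patients

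Up to 21, every such patient falls below the sample median whatever their true age. At exactly 21, the lower group consists only of patients with incomplete birth dates, so the split separates patients by completeness of the record and not by age. Above 21, the median itself is 0, nobody is below it, and the split fails.

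**Step 4: primary endpoints.** The VAS change and the DMRQ proportion (SAP 5.6.1) use neither age nor any imputed date. They do not change.

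**The case against.** The strongest reply is that a specific rule should prevail over a general one. The birth sentence states the value to be analysed, and under the limit it could never have effect in an adult trial. The sensible reading keeps it and confines the limit to on-study events; the paragraph that follows, on death, points the same way. An age of 0 would also show itself, because SAP 5.1.1 reports the minimum of continuous variables. And age feeds only a descriptive table and a subgroup analysis meant to show consistency.

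Most of this stands. The limit was probably meant for on-study events, and the error would probably be noticed. But nothing in the text says so. The authors added a type-specific condition for death and none for birth, so the plan works here only if part of it is disregarded.

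It also stands that the frequency is unknown. The protocol says only that demographics are collected. If age is recorded directly, or every birth date is complete, nothing is affected.

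A reader might go further and infer that long-standing illnesses or medicines, including those that cause dry mouth, would appear to have started at study entry. The documents do not support that. Protocol 9.12 says "Concomitant medications should be collected at Visit 1" but does not mention start dates. The SAP plans no analysis of concomitant medication, SAP 5.5 promises summaries of medical history without mentioning onset dates, and the listings in SAP 7 cover only protocol deviations and side effects or adverse events. Year-only dates other than birth are queried with the site, so only month-and-year dates could move, and no planned output is shown to use them.

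**Conclusion.** The point holds as an internal contradiction in SAP 5.3: followed as written, any patient with an imputed birth date gets age 0. It is minor. It can affect the age summary and the median-age subgroup analysis, and leaves the primary VAS and DMRQ estimates untouched.

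The zero follows from the text and the adult age criterion, given that age is derived from date of birth. The number of patients affected does not follow from the documents; the 10%, 20% and 50% shares and the true mean of 60 are assumptions that show scale only. The documents also give no ground for concluding that ages in this trial were in fact set to 0.

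**What to change.** In SAP 5.3, limit the Visit 1 condition to events that can only occur during the study, such as onset of a treatment-emergent adverse event or death. State that it does not apply to date of birth or, if they are collected, to other dates that properly precede Visit 1.

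The change is one sentence. SAP version 1.1 was written after database lock, so the sentence would need either an approved SAP amendment or an entry in the clinical study report, as SAP 6 provides. Whether any birth date is partial can be checked in the locked data. If analyses have already been run, the report should confirm that no age was derived from a birth date replaced by Visit 1. No new data are needed.

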5.4 Subject Disposition

The number of subjects in each analysis population will be presented along with reason for any exclusions. Subject accountability will be summarized by visit. The number of subjects who are enrolled, eligible for follow-up, and number completing clinical follow-up will be summarized for each visit specified in the protocol. In addition, the number of subjects who complete the study or exit early will be summarized by reason.

5.5 Demographics and Baseline Characteristics

Descriptive statistics will be presented for all clinically relevant baseline demographic, medical history, and clinical characteristic variables.

5.6 Analysis of Study Endpoints

5.6.1 Primary Analysis

The primary endpoint will be examined in the following hypothesis:

- Null hypothesis
Change in VAS after MucoPEG minus change in VAS after Biotène ≥ 0
- Alternative hypothesis
Change in VAS after MucoPEG minus change in VAS after Biotène < 0

Statistical Analysis Plan		Page 15 of 17
Sponsor SunBio Inc.	Study Clinical Evaluation of MucoPEG for Xerostomia	Version 1.1

The change in VAS associated with each product will be calculated as the value of VAS at two hours after the final dose at Visit 4 minus the value of VAS before the first dose at Visit 2 for the first treatment period. Since the Visual Analogue Scale is constructed such that 0 = no symptom and 10 = most severe symptom, an improvement in symptom is represented by a negative change in its measurement. The hypotheses are to test whether patients would experience greater improvement in their symptoms after a course of MucoPEG.

The change in VAS for the second treatment period will be calculated in a similar way from the value of VAS before the first dose at Visit 5 and the value of VAS at two hours after the final dose at Visit 7.

This set of hypotheses will be tested in a one-sided test of difference between two means, for each treatment period, to examine whether a greater change in VAS is associated with MucoPEG than with Biotène. Interval estimation will be carried out using the t distribution and the objective will be met if the upper limit of a 90% confidence interval of the difference is less than zero.

The primary endpoint will also be examined in the following hypothesis:

- Null hypothesis
The proportion of patients with a favourable response after MucoPEG minus the proportion of patients with a favourable response after Biotène ≤ 0
- Alternative hypothesis
The proportion of patients with a favourable response after MucoPEG minus the proportion of patients with a favourable response after Biotène > 0

The numerator will be the number of patients who responded with “4 – very good” or “5 – significant / excellent” in the Dry Mouth Relief Questionnaire. The denominator will be the number of patients eligible for taking the Dry Mouth Relief Questionnaire. Patients with missing outcome status will be reported as a separate category. Change in proportions between Visit 2 and Visit 4 in the first treatment period and between Visit 5 and Visit 7 in the second treatment period will be assessed.

This set of hypotheses will be tested in a one-sided test of difference between two proportions, for each treatment period, to examine whether a greater proportion is associated with MucoPEG than with Biotène. Interval estimation will be carried out using an exact method for binomial outcomes and the objective will be met if the lower limit of a 90% confidence interval of the difference is greater than zero.

The endpoint will be evaluated by analysing the data from the intent-to-treat set. The endpoint will be presented as the mean difference in scores and its one-sided confidence interval for change in VAS and as mean difference in proportions for ratings from the Dry Mouth Relief Questionnaire.

Statistical Analysis Plan		Page 16 of 17
Sponsor SunBio Inc.	Study Clinical Evaluation of MucoPEG for Xerostomia	Version 1.1

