5 INVESTIGATIONAL DEVICE DESCRIPTION

MucoPEG™ received FDA clearance on November 5, 2019 with the 510(k) number K190144. MucoPEG™ is an artificial saliva. The main ingredient of MucoPEG™ is a polyethylene glycol (PEG) derivative. This PEG derivative forms a covalent bond with the oral epithelial cell. The

additives to MucoPEG™ are mint (for flavor) and sodium bicarbonate (for pH maintenance when dissolved in water).

MucoPEG™ is available by prescription for home use. It is formulated as a powder and packaged in a single-use packet, which should be kept in a dry environment and stored in the freezer between -4 ± 9 °F. The shelf-life is expected to be one year under the prescribed environment. MucoPEG™ is not sterile and conforms with ISO 10993-1 for cytotoxicity, sensitization, and irritation.

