9.9 Washout Period

Patients will be required to undergo a washout period twice during the study. The first washout period should occur after the subject signs consent and will last until the baseline visit (Visit 2). The second washout period will start after the end of Visit 4 and last until the beginning of Visit 5. A washout period is necessary to ensure patients proceed to a new treatment period without carrying over any residual effects from previous treatment. During the washout period patients will be instructed *not* to use any over the counter or prescription products for dry mouth. Patients will be allowed to only use water to rinse their mouth during the washout period. If a patient uses any type of oral rinse to treat dry mouth during the washout period it will be considered a protocol deviation.

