15.3 Statistical Methods

Data will be summarised descriptively as tables and/or graphs. Continuous variables such as patient’s assessment of mouth dryness using the Visual Analogue Scale (VAS) are to be summarised as mean, standard deviation, number of non-missing observations, median, minimum and maximum by the product used (MucoPEG™ or Biotène® Dry Mouth Gentle Oral Rinse) and period (1 – before washout or 2 – after washout). Discrete variables such as ordinal

responses or binary responses (yes or no) from the Dry Mouth Relief Questionnaire, the Product Performance and Attributes Questionnaire, etc. are to be summarised as frequency counts and percentages by product and period.

Measurements of symptom severity will be tested in a Student's t test for the difference between MucoPEG™ and Biotène® Dry Mouth Gentle Oral Rinse in their mean changes in Visual Analogue Scale for each treatment period. Changes between Visit 2 and Visit 4 and between Visit 5 and 7 will be tested for the primary endpoint and changes between Visit 2 and Visit 3, between Visit 5 and Visit 6, within Visit 2 (before the first dose and two hours after the first dose) and Visit 5 (before the first dose and two hours after the first dose) will be tested for the secondary endpoint. Confidence intervals will be presented with significance probability of the difference between the mean values.

Data on other secondary endpoints will be summarised descriptively.

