3.3 Study Assessments

Patients are considered to be enrolled in this study after placing their signature on the consent form at Visit 1. Their eligibility to proceed and their concomitant medications will then be checked. Before Period 1 (the first use of MucoPEG or Biotène), patients will undergo one week of “washout” period.

During Period 1, which will last for two weeks, patients will use one of the products twice daily and will be assessed on the first day (Visit 2), seventh day (Visit 3) and fourteenth day (Visit 4) using the VAS, DMRQ, DMI, PPAQ, PPUQ. Information from symptom diary, medications, clinical examination and adverse events will also be recorded.

Another washout period of one week follows Period 1. The assessments for the second treatment will have the same pattern, with Visit 5, 6 and 7 to take place within Period 2.

4 Sample Size Determination

The hypotheses for this study are

- Null hypothesis
Change in VAS after MucoPEG minus change in VAS after Biotène ≥ 0
- Alternative hypothesis
Change in VAS after MucoPEG minus change in VAS after Biotène < 0

The change in VAS associated with each product will be calculated as the value of VAS at two hours after the final dose at Visit 4 minus the value of VAS before the first dose at Visit 2 for the first treatment period. Since the Visual Analogue Scale is constructed such that 0 = no symptom and 10 = most severe symptom, an improvement in symptom is represented by a negative change in its measurement. The hypotheses are to test whether patients would experience greater improvement in their symptoms after a course of MucoPEG.

Statistical Analysis Plan		Page 12 of 17
Sponsor SunBio Inc.	Study Clinical Evaluation of MucoPEG for Xerostomia	Version 1.1

The change in VAS for the second treatment period will be calculated in a similar way from the value of VAS before the first dose at Visit 5 and the value of VAS at two hours after the final dose at Visit 7.

Assuming the average difference between randomization groups is -1.25, a common standard deviation of 1.50 and a Type I error of 0.05 (one-sided probability), an effective sample size of 38 patients will provide 80% power to reject the null hypothesis of no difference between the two products (MucoPEG versus Biotène).

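### The primary VAS test uses raw change with no baseline covariate, and nothing checks that Visit 5 VAS returned to its Visit 2 level; unequal residues that fade would bias Period 2

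*SAP*

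**What the plan says.** SAP 5.6.1 defines the Period 1 change as VAS two hours after the final dose at Visit 4 minus VAS before the first dose at Visit 2. The Period 2 change "will be calculated in a similar way from the value of VAS before the first dose at Visit 5"; its end point is the rating made two hours after dosing at Visit 7. The analysis is a "one-sided test of difference between two means, for each treatment period", and the objective is met if the "upper limit of a 90% confidence interval of the difference is less than zero". Protocol 15.3 likewise names a Student's t test for the difference between products "in their mean changes in Visual Analogue Scale for each treatment period". SAP Section 4 fixes the direction of the scale ("0 = no symptom and 10 = most severe symptom"), so improvement is a negative change.

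The safeguard against carry-over is the washout. Protocol 9.9 states: "A washout period is necessary to ensure patients proceed to a new treatment period without carrying over any residual effects from previous treatment". Protocol Section 5 describes the investigational product: "This PEG derivative forms a covalent bond with the oral epithelial cell". It gives no duration of effect.

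The other planned analyses do not address the point. SAP 5.6.2 concerns missing responses, SAP 5.2 adds the per protocol set, and the only regression (SAP 5.9) contains treatment, subgroup and their interaction. Neither document names a baseline covariate, a sequence or carry-over term, or a comparison of Visit 5 with Visit 2.

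**The concern.** In Period 2 the Biotène users are Group A, who took MucoPEG first. If some MucoPEG effect remained at Visit 5, their starting VAS would be lower and their later improvement on Biotène would look smaller. MucoPEG minus Biotène would become more negative, which is the direction the success rule rewards. The protocol treats residual effect as a risk, since it gives that as the reason for the washout, but plans no look at whether the washout worked. The SAP also does not say whether one or both period tests must succeed, so a favourable Period 2 result could carry weight alone.

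There is a second, simpler loss. Pre-dose VAS is collected at Visits 2 and 5, and the planned test uses it only by subtraction. Adjusting for it would normally give a more precise comparison. In Period 1 that gain carries no carry-over risk.

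**Working it through.** **1. The plan's own figure.** Inputs from SAP Section 4: difference −1.25, SD 1.50, one-sided 5%, 38 patients, 80% power. Protocol 15.2 gives 1:1 allocation, so 19 per group. Standard error = 1.50 × √(2/19) = 0.487. Noncentrality = 1.25/0.487 = 2.57, with 36 degrees of freedom and critical t 1.688. Power is 80.9%, so 38 reproduces as a between-group test, the form used within each period.

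**2. Bias in raw change.** Let c be the MucoPEG residue minus the Biotène residue at Visit 5, in VAS points, and p the share of it still present at Visit 7. In Period 2, Group A (now on Biotène) minus Group B (now on MucoPEG) differs through residue by −c at Visit 5 and −pc at Visit 7. The bias in MucoPEG minus Biotène is therefore −c(1 − p).

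The documents give neither c nor p; both are assumptions here. With no true difference, the noncentral t with shift c(1 − p)/0.487 gives:

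| Net residue c | Share left at Visit 7, p | Bias | False-positive rate |
|---|---|---|---|
| 0 (none, or equal residues) | any | 0 | 5.0% |
| 0.25 | 0 | −0.25 | 12.7% |
| 0.5 | 0 | −0.50 | 26.2% |
| 1.0 | 0 | −1.00 | 64.5% |
| 0.5 | 0.5 | −0.25 | 12.7% |
| 0.5 | 1 | 0 | 5.0% |
| −0.5 (Biotène residue larger) | 0 | +0.50 | 0.4% |

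**3. Adjusting for pre-dose VAS.** Let r be the pre/post correlation (assumed 0.5, range 0.3 to 0.7), with equal SDs before and after. A change SD of 1.50 implies a VAS variance of 2.25/(2(1 − r)) and a residual SD of 1.50 × √((1 + r)/2): 1.21, 1.30 and 1.38 for r = 0.3, 0.5 and 0.7. Power for −1.25 without carry-over is then 93%, 90% and 86%, against 81% unadjusted.

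With carry-over, the adjusted bias is −c(r − p). For c = 0.5 and r = 0.5:

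- p = 0: bias −0.25 and false-positive rate about 14% (10% to 19% over the range of r), against 26% unadjusted.
- p = 0.5: bias 0, against −0.25 unadjusted.
- p = 1: bias 0.25 against MucoPEG, where raw change has none; power for −1.25 falls to about 75%.

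At r = 0.5 the covariate leaves more bias than raw change once p exceeds 0.75, where p − 0.5 passes 1 − p.

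**4. What a Visit 5 table can show.** With 19 per group and an SD of 1.5 (assumed), the 90% interval for the difference between sequences has half-width 1.688 × 0.487 = 0.82 points. Used as a test at two-sided 10%, it has about 27% power for 0.5 points and 66% for 1.0. It is informative as an estimate and weak as a gatekeeper.

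**5. Length of washout.** Protocol Table 1 allows Visit 4 up to Day 16 and Visit 5 from Day 22: 22 − 16 = 6 days. The nominal gap is 22 − 14 = 8 days. The footnote to the same table requires at least 7.

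**The case against.** The strongest reply is that no residue is documented. The covalent-bond statement comes without a duration, and Protocol 5.2 describes a water rinse after each use to remove residual product. The larger error rates also need a net residue in MucoPEG's favour that has gone by Visit 7; other patterns give no bias or the opposite bias. All of this stands. A reader might infer that Period 2 is biased or that carry-over is likely. The documents support only that it is possible and unchecked.

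Second, the tests are run by period, so a carry-over-free Period 1 result is already planned, and Protocol 15.3 summarises VAS by product and period. That helps, but no section commits to showing pre-dose VAS at Visit 5 against Visit 2, or says how Period 2 should be read.

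Third, the unadjusted t-test is valid under randomisation in Period 1 and matches the sample-size basis. SAP v1.1 also records changes made after database lock, one of them after the sponsor had examined some results. This stands against replacing the primary test; it does not stand against a labelled additional analysis.

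Fourth, disagreement between periods would be a poor trigger for preferring Period 1. With 80.9% power in each, and treating the periods as independent (an assumption), exactly one is significant with probability 2 × 0.809 × 0.191 = 31% without any carry-over. This is accepted: Period 1 should be named as the carry-over-free result regardless of agreement.

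Finally, one might read Table 1 as simply permitting a six-day washout. Its footnote says otherwise, so the finding is an internal inconsistency.

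**Conclusion.** The point holds as a conditional one. It is established from the documents that the primary test uses raw change, omits the available covariate, and is accompanied by no check that Visit 5 VAS returned to its Visit 2 level. The Period 2 false-positive rates of 12.7%, 26% and 64% rest on assumed net MucoPEG residues of 0.25, 0.5 and 1.0 points that have fully faded by Visit 7, with 19 per group and SD 1.50. Period 1 is unaffected by carry-over.

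The precision gain, from 81% power to about 90%, assumes no carry-over, equal SDs before and after, and a correlation near 0.5. It should not be inferred that the covariate cures carry-over: in Period 2 it may reduce the bias, leave it or reverse it, depending on how much residue persists.

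**What to change.** 1. In SAP 5.6.1, add for each period a model of end-of-period VAS on treatment, with that period's pre-dose VAS as covariate. Report it beside the planned t-test and label it post hoc, because SAP v1.1 follows database lock.
2. Tabulate Visit 5 minus Visit 2 pre-dose VAS by first product, with the difference between sequences and its confidence interval. Present it as an estimate; do not use it as a pre-test to choose the analysis.
3. State that Period 1 is the carry-over-free result and that Period 2 is to be interpreted in light of that table, whether or not the covariate is used.
4. Reconcile the Table 1 windows for Visits 4 and 5 with its washout footnote, and report the actual gap for each patient.

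The cost is a few sentences in the SAP, one model per period and one table, with a listing of gaps, all from data already collected. The limitation is that the additions are post hoc and so support interpretation without changing the planned success rule.
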